4. PARTICIPANT SELECTION

Potential participants will be screened and recruited from the University of Alabama at Birmingham, University of Wisconsin, University of Minnesota, University of Iowa and Northwestern University. Beginning in November of 2021, study sites will be limited to University of Alabama at Birmingham, University of Wisconsin, and Northwestern University.

4.1 Inclusion Criteria

1. Female only. The sample size of males affected by breast cancer is limited, hence we will not be able to collect significant data for analysis of the effect of study drug on breast cancer in males
2. Age \geq 18 years. Because no dosing or adverse event data is currently available on the use of 9cUAB30 in participants <18 years of age.
3. ECOG performance status ≤ 1 or Karnofsky $\geq 70\%$ (convert the Karnofsky score into the ECOG scale based on Appendix A).
4. Invasive breast cancer diagnosed by needle core biopsy, between 0.5 cm and 5 cm in size based on imaging, that is ER+ or ER-, Her2neu positive or negative

OR

DCIS of the breast diagnosed by core needle biopsy and at least 1.0 cm in size based on imaging. Grade 3 ER+ DCIS will be allowed as well as ER- DCIS of any grade. For DCIS-only lesions, the imaging abnormality corresponding to the cancer must be at least 1.0 cm in size (i.e. calcifications, distortion or mass on mammogram, or mass or nonmass enhancement on MRI).

5. Participants must have normal organ and marrow function as defined below:
 - WBC $\geq 3000/\text{mm}^3$;
 - Platelets $\geq 100,000/\text{mm}^3$,

- Hemoglobin >10 g/dL;
- Bilirubin \leq upper limit of institutional normal;
- AST \leq upper limit of institutional normal
- Creatinine \leq upper limit of institutional normal
- Triglycerides \leq 1.5xULN
- Cholesterol \leq 1.5xULN

6. Participants must agree to discontinue all supplements containing vitamin A while taking study medication and for thirty days after the last dose of study medication.
7. Have not been treated with chemotherapy, or biological therapy in the last 5 years. We do not know if the previous treatment will have an effect on the tissues to be examined.
8. Have not used tamoxifen, raloxifene, or other antiestrogen compounds within 6 months of study entry. If used within 5 years of study entry, total duration of use must be less than 6 months.
9. Have not used exogenous hormone replacement therapy or hormonal contraception in the year prior to diagnosis. The use of non-systemic estrogen (such as vaginal estrogen use) is allowed.
10. The effects of 9cUAB30 on the developing human fetus are unknown. Since retinoids are known to be teratogenic, to avoid any complications due to unintentional pregnancies only postmenopausal women and some premenopausal women (as outlined below) will be eligible. Should a woman become pregnant or suspect she is pregnant while participating in this study, she should inform her study physician immediately.
 - Women will be considered postmenopausal if one of the following is met:
 - i. Prior bilateral oophorectomy
 - ii. 60 years of age or older
 - iii. Age less than 60 years; amenorrheic for 12 or more months; and follicle-stimulating hormone (FSH) in the postmenopausal range or had prior hysterectomy.
 - Premenopausal women without childbearing potential are eligible to participate if one of the following criteria is met:
 - i. Prior hysterectomy
 - ii. Prior fallopian tubal ligation (cut, tied, or sealed)
 - iii. Prior placement of permanent intratubal contraceptive devices (e.g. Essure)
 - iv. Partner with prior vasectomy and willing to use barrier method (e.g. condoms)
11. Participants must have the ability to understand, and the willingness to sign, a written informed consent document.

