4.2 Exclusion Criteria

1. Participant taking medications that might interact with 9cUAB30; See section 5.4 for a detailed list of potentially interacting medications
2. Participant who has started or increased dosage of lipid-lowering agents in the last 30 days of enrollment.
3. Participant receiving any other investigational agents within 30-days of enrollment nor during study participation with the exception of ^{18}F -FFNP investigational imaging agent. See section 5.4 for a detailed description of ^{18}F -FFNP trial co-enrollment conditions.
4. Participant with a history of allergic reactions attributed to compounds of similar chemical or biologic composition of retinoids.

5. Participant with an uncontrolled intercurrent illness including, but not limited to:
 - a. ongoing or active infection,
 - b. symptomatic congestive heart failure,
 - c. unstable angina pectoris,
 - d. cardiac arrhythmia,
 - e. a persistent grade 3 hypertension***
 - f. psychiatric illness/social situations that will limit compliance with study requirements.
6. Participant who is breastfeeding or planning to breastfeed for a month post last dose of study agent
7. Participant known to be HIV-positive, as we do not know the effects of study drug on suppression of the immune system.
8. Participant with a history of a second cancer diagnosis or reoccurrence <2 years from study entry with the exception of a history of squamous or basal cell carcinoma of the skin <2 years from study entry will not be excluded from this study. This is to eliminate the residual effects of any previous treatments for those cancers.
9. Participant with history of ipsilateral breast radiation.
10. Participant's core biopsy slides suggest that later re-sectioning will not contain sufficient tumor to allow for an adequate evaluation of Ki67 and caspase 3 assays, at a minimum.

***To assess hypertension during eligibility verification, see below instructions:

For grade 1, grade 2, and non-persistent grade 3 hypertension, repeat blood pressure reading after 5 minutes. If the average reading of the two measurements is grade 3 (systolic BP \geq 160 mm Hg or diastolic BP \geq 100 mm Hg) the patient is not eligible. If the average reading of the two measurements is less than or equal to grade 2, then the participant is eligible. If the average of the 2 readings is grade 1 or grade 2 hypertension, document the appropriate level hypertension on the baseline symptom form.

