7. CLINICAL EVALUATIONS AND PROCEDURES

7.1 Schedule of Events

Evaluation/ Procedure	Screening Visit	Day 1	Day 7	Day 8 (± 1 Day)	Day before surgery (-2 Days)	Surgery Day 15-29	7 days after surgery (± 1 Day)	4-5 weeks after surgery
Informed consent	X							
Assess eligibility	X							
Medical history	X							
Physical exam	X					X		
Vital signs/ height and weight	X ¹		X ²	X ²	X ²	X ¹⁰		
Laboratory tests ³								
- CBC with differential								
- PTT, INR								
- CMP						X ⁴		
- TSH/FT3/FT4								
- HDL/LDL/Chol/TG								
- FSH ⁵								
Urine for PK	X					X		
Plasma for PK	X	X ⁶				X		
Immunogenicity sample	X ⁷					X ⁷		
Concomitant medications	X			X	X	X	X	X
Dispense study agent	X							
Study medication start		X						
Collect study agent						X		
Providing drug diary and instructions	X							
Provide Blood Pressure monitors	X							
Review agent diary/record						X		
Adverse events	X			X	X	X	X	X
Telephone contact				X	X		X	X
Tobacco and Alcohol assessments	X ⁸					X ⁹		

1. Participant will be given a BP monitor, instructed on its use, and given instructions on recording and reporting BP readings. See section 11.1.1 Reportable AEs, for how the blood pressure should be obtained.
2. Home BP check (morning) only. For Day 7 and Day 8, the readings should be approximately 24 hours apart. If the participant has missed taking their BP reading on Day 7 and Day 8 they should be encouraged to note two readings on the following days at least 24 hours apart from each other.
3. CBC with differential will include WBC, differential, platelets, hemoglobin and hematocrit. CMP will include electrolytes (Na, K, Cl, CO₂) glucose, BUN, creatinine, calcium, albumin, total bilirubin, AST, ALT, alkaline phosphatase.
4. Participant must be fasting for 10 hours for the surgery Day 15-29 lab collection.
5. FSH will be collected for confirmation of post-menopausal status at screening for women under 60 who are amenorrheic for 12 or more months.
6. For first 5 participants only, plasma PK samples will be collected 5 minutes and 2 hours after the first dose has been administered.
7. For participants 6-25.
8. Appendix D – administer the baseline version of tobacco and alcohol assessments

9. Appendix D – administer the follow-up version of tobacco and alcohol assessments
10. Blood pressure on Surgery Day 15-29 will only be obtained if the Day before Surgery average blood pressure is above Systolic ≥ 120 or Diastolic ≥ 80 .

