7.2 Baseline Testing/Prestudy Evaluation

7.2.1 Screening Visit (within 30 days of Day 1)

Newly diagnosed early stage breast cancer patients will be screened as potential participants from the University of Alabama at Birmingham, University of Wisconsin, University of Minnesota, University of Iowa, and Northwestern University. A history and physical examination will be performed as part of standard of care by providers at each institution.

The procedures to be performed to evaluate eligibility are:

- Invasive breast cancer or DCIS confirmed on pathology report; eligible participants must have invasive breast cancer between 0.5 cm and 5.0 cm in size based on imaging or for DCIS-only lesions, the imaging abnormality corresponding to the cancer must be at least 1.0 cm in size (i.e. calcifications, distortion or mass on mammogram, or mass or nonmass enhancement on MRI).
- Estrogen receptor status must be confirmed on pathology report. Estrogen receptor positivity defined as per 2010 ASCO-CAP Guidelines³⁶ – with at least 1% positive tumor nuclei in the sample on testing in the presence of expected reactivity of internal (normal epithelial elements) and external controls.
 - Eligible participants must have invasive breast cancer that is ER+ or ER-,
OR
 - Eligible participants must have DCIS that is ER+ and grade 3, or that is ER- and any grade.

*Beginning in November 2021, participants will be limited to estrogen receptor negative status.

- Her2neu status must be confirmed on pathology report for those with invasive cancer.³⁷ Her2neu status is defined as positive and negative based on the 2013 ASCO-CAP guideline. As recommended by the guideline, Her2neu equivocal results must have a reflex or new test to determine Her2neu status.
- Review of the participant's medical history.
- Measurement of height and weight.
- Evaluation of vital signs including temperature, pulse, blood pressure, and respiration rate.
 - For grade 1, grade 2, and non-persistent grade 3 hypertension, repeat blood pressure reading after 5 minutes.
 - If the average reading of the two measurements is grade 3 (systolic BP ≥ 160 mm Hg or diastolic BP ≥ 100 mm Hg) the patient is not eligible.
 - If the average reading of the two measurements is less than or equal to grade 2, then the participant is eligible.
 - If the average of the 2 readings is grade 1 or grade 2 hypertension, document the appropriate level hypertension on the baseline symptom form.

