- A physical examination. A gynecologic examination may be waived. The physical examination may be performed by any healthcare professional (i.e. physician, nurse practitioner, physician assistant) who is allowed by local policy to perform physical examinations.
- Assessment of Performance Status, using the ECOG method (convert a Karnofsky score into an ECOG score using the scale in Appendix A).
- Review of concomitant medications including over the counter medications and nutrition supplements
- Review and discussion of study including review of informed consent document.

- Patients agreeing to participate in the study will sign the informed consent document.

After obtaining written informed consent, a participant is registered with CLO and assigned a unique PID number (see section 6.8) and eligibility evaluations may occur. Eligibility evaluations determine if the participant is a fit candidate for study participation. All eligibility evaluations (including labs) must be completed within 30 days of Day 1. The eligibility checklist is provided to each site to help determine if the participant is eligible for the trial.

- Administer the baseline version of tobacco and alcohol assessment questionnaire – Appendix D
- Perform the laboratory tests as outlined in section 7.1. Results from laboratory tests or physical examinations performed outside the context of the research study may be used to confirm eligibility, provided these procedures were conducted within 30 days of Day 1.
- A fasting or non-fasting lipid panel may be obtained, if drawn within 30 days of Day 1. If non-fasting lipid levels are outside of the range for eligibility, a fasting lipid panel can be drawn. For the fasting lipid panel, participants should be fasting for at least 10 hours prior to this draw.
- Collect urine and blood sample for baseline PK studies.
- Collect 30 mL blood sample for immune studies for participants 6-25.

If deemed eligible, follow the below mentioned procedures:

For the first 5 participants:

- a. Since the participants will be fasting for the laboratory tests, they can have a meal after blood draw for laboratory tests while they wait to get their laboratory results.

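### No pregnancy test is specified before the first dose for premenopausal women who enter under criterion 10(iv), although criterion 10 exists to prevent fetal exposure

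*Combined protocol and SAP*

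**What the plan says.** Section 4.1, criterion 10 gives its reason for restricting entry: "Since retinoids are known to be teratogenic, to avoid any complications due to unintentional pregnancies". Postmenopausal women are admitted, and for the others the rule is "Premenopausal women without childbearing potential are eligible to participate if one of the following criteria is met". Items i to iii are hysterectomy, tubal ligation and a permanent intratubal device. Item iv is "Partner with prior vasectomy and willing to use barrier method (e.g. condoms". The same criterion adds: "Should a woman become pregnant or suspect she is pregnant while participating in this study, she should inform her study physician immediately".

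Section 7.1 contains one laboratory test of reproductive status: "FSH will be collected for confirmation of post-menopausal status at screening for women under 60", limited to those with at least 12 months of amenorrhea. Section 7.2.1 refers to 7.1 for the laboratory tests. Its clinical checks include "Review of the participant's medical history" and "A physical examination. A gynecologic examination may be waived".

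Section 4.2, item 6 excludes a "Participant who is breastfeeding or planning to breastfeed for a month post last dose of study agent". Pregnancy itself appears in 8.4 and 8.5, as a reason for stopping the agent or leaving the study.

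**The concern.** Items i to iii each depend on a procedure in the participant herself. Item iv depends on a procedure in her partner and on her willingness to use a barrier method. The vasectomy needs no stated minimum interval or proof of success, and willingness looks forward, so it says nothing about a pregnancy already present at screening. Inclusion criterion 9 also rules out hormonal contraception in the year before diagnosis, so these women will not have been using it recently.

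At stake is exposure of a fetus to 14 to 28 daily doses of an agent whose fetal effects the protocol calls unknown. This is a participant-safety matter and does not bear on the Ki-67 analysis or its power.

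**Working it through.** No formula applies. The check is whether any step before the first dose would detect a pregnancy that the woman does not know about.

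| Place | What it provides | Would it detect an unrecognised pregnancy before Day 1? |
|---|---|---|
| Section 3, baseline laboratory tests | Blood count, coagulation, chemistry, lipids, thyroid | No |
| 7.1, laboratory rows and footnotes | Six lines: CBC, PTT/INR, CMP, thyroid, lipids, FSH | No; none is an hCG test, and the listed CMP content has none |
| 7.2.1, clinical checks | History; physical examination, gynecologic part may be waived | Not reliably |
| 7.2.1, urine and blood at screening | Collected for pharmacokinetics, plus immune studies in participants 6-25 | No, but suitable material is in hand |
| 7.3.1, Day 1 | Start of dosing | No test listed |
| 4.1(10), self-report | Applies during participation, if pregnancy occurs or is suspected | No |
| 8.4 and 8.5 | Pregnancy as a reason to stop agent or leave study | No; they follow entry or exposure |

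The result is six laboratory lines in 7.1 and no pregnancy test among them. The table was extracted from PDF and some of its marks are lost, but the row labels and footnotes that name the tests are intact.

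**Timing.** Section 7.3.1 recommends starting drug promptly once eligibility is settled, and 7.2.1 lets participants 6 onward start on the evening of dispensing. Screening is therefore the practical control point. Eligibility evaluations may nevertheless be as much as 30 days old on Day 1. That is a worst case, but it shows why a test needs its own window.

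**Number of women.** The documents give no count of item iv entrants. The Schema gives 12 ER-negative participants under the restriction that began in November 2021. Sections 13.1 and 13.2 give the same 12 as the ER-negative target for the whole trial, so some may already be enrolled. Item iv entrants are a subset of the premenopausal women among them. The prospective range is thus 0 to 12, with 12 a loose ceiling. It bounds cost: at most 12 × 1 = 12 tests, or 12 × 2 = 24 if every test were repeated once. It does not estimate risk.

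**The case against.** Several counter-arguments have force.

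- **Known pregnancy is already barred.** A woman known to be pregnant cannot satisfy a criterion that admits only premenopausal women who lack childbearing potential. This stands. A reader might infer from the silence of 4.2, which names breastfeeding but not pregnancy, that the protocol allows pregnant women to enter. The documents do not support that: the inclusion wording, the stated purpose of criterion 10, and 8.4 and 8.5 all point the other way. The missing line in 4.2 is not a separate defect.
- **The risk may be very small.** A pregnancy at Day 1 would require a failed vasectomy or conception outside that partnership. This also stands, and there may be no item iv entrants at all. The case rests on the gravity of the harm and the low cost of the check.
- **Sites may already test.** Section 7.2.1 mentions an eligibility checklist that is not in the file, and the consent pages were removed. The laboratory lists are also not fully aligned: Section 3 omits the FSH that 7.1 requires. A reader might infer that sites dose these women with no check at all; the documents show only that the protocol specifies none. Equally, an unseen form cannot be assumed to supply the test.
- **Item iv is not the only route that leaves uterus and ovaries in place.** Women under items ii and iii may keep both, and nothing in the documents ranks the reliability of the methods. Whether to test them is a clinical judgement.

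**Conclusion.** The point holds as a gap in verification. Criterion 10 aims to prevent fetal exposure, item iv admits premenopausal women who may be fertile, and the protocol text specifies no pregnancy test before their first dose. The existing safeguards depend on the woman already suspecting pregnancy, or they act after entry or exposure.

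It is a cheap safety improvement for a small number of women. The probability of harm cannot be estimated from the documents, and no power, endpoint or analysis figure changes. The conclusion assumes that the protocol text is the governing instruction to sites, and it makes no claim about local practice.

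**What to change.** Add to 7.1 and 7.2.1 a negative urine or serum hCG before the first dose for women who enter under item iv. The sponsor's clinicians should set the window before Day 1, with a repeat if Day 1 falls outside it, and should decide whether item ii and iii entrants are also tested. The urine or blood already taken at screening can be used; 10.2.3 has sites discard any urine left after the pharmacokinetic aliquot. The eligibility checklist should carry the same item. A pregnancy line in 4.2 may be added as conforming wording. The heading above items i to iv should stay as it is, since it bars known pregnancy.

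The cost is a short amendment and one inexpensive test for each woman concerned. The one practical burden is that participants 6 onward have no scheduled clinic visit between dispensing and Day 1, so an occasional repeat would need a brief visit or a home kit.

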4.2 Exclusion Criteria

1. Participant taking medications that might interact with 9cUAB30; See section 5.4 for a detailed list of potentially interacting medications
2. Participant who has started or increased dosage of lipid-lowering agents in the last 30 days of enrollment.
3. Participant receiving any other investigational agents within 30-days of enrollment nor during study participation with the exception of ^{18}F -FFNP investigational imaging agent. See section 5.4 for a detailed description of ^{18}F -FFNP trial co-enrollment conditions.
4. Participant with a history of allergic reactions attributed to compounds of similar chemical or biologic composition of retinoids.

5. Participant with an uncontrolled intercurrent illness including, but not limited to:
 - a. ongoing or active infection,
 - b. symptomatic congestive heart failure,
 - c. unstable angina pectoris,
 - d. cardiac arrhythmia,
 - e. a persistent grade 3 hypertension***
 - f. psychiatric illness/social situations that will limit compliance with study requirements.
6. Participant who is breastfeeding or planning to breastfeed for a month post last dose of study agent
7. Participant known to be HIV-positive, as we do not know the effects of study drug on suppression of the immune system.
8. Participant with a history of a second cancer diagnosis or reoccurrence <2 years from study entry with the exception of a history of squamous or basal cell carcinoma of the skin <2 years from study entry will not be excluded from this study. This is to eliminate the residual effects of any previous treatments for those cancers.
9. Participant with history of ipsilateral breast radiation.
10. Participant's core biopsy slides suggest that later re-sectioning will not contain sufficient tumor to allow for an adequate evaluation of Ki67 and caspase 3 assays, at a minimum.

***To assess hypertension during eligibility verification, see below instructions:

For grade 1, grade 2, and non-persistent grade 3 hypertension, repeat blood pressure reading after 5 minutes. If the average reading of the two measurements is grade 3 (systolic BP \geq 160 mm Hg or diastolic BP \geq 100 mm Hg) the patient is not eligible. If the average reading of the two measurements is less than or equal to grade 2, then the participant is eligible. If the average of the 2 readings is grade 1 or grade 2 hypertension, document the appropriate level hypertension on the baseline symptom form.

4.3 Inclusion of Women and Minorities

Women of all races and ethnic groups are eligible for this trial.

4.4 Recruitment and Retention Plan

Potential participants will be screened and recruited from the University of Alabama at Birmingham, University of Wisconsin, University of Minnesota, University of Iowa and Northwestern University. Breast cancer surgeon investigators at each site will be instrumental in achieving accrual targets. The duration of the accrual is expected to take 18- 24 months. Beginning in November of 2021, study sites will be limited to University of Alabama at Birmingham, University of Wisconsin, and Northwestern University.

Each site will review the surgeon's clinic patient list to identify potential participants. Through review of the medical record, the study team will determine if a patient is eligible and contact them for interest in the study. Review of medical records prior to consenting to the research study is very minimum risk of harm to the potential study participants and involves no study related procedures for which written consent is normally required outside of the research context.

The potential participant may be initially approached by their physician and the study coordinator will then speak with them more in depth about the study.

We plan to have staggered enrollment for the study. We will enroll 5 participants at the 240mg dose level

and after analysis of the PK data collected from the first 5 participants, it will be determined whether to continue with 240mg dose level or to modify the dose to 160mg for rest of the study. If the study continues at 240mg dose level, the remaining 31 participants will be accrued. If the dose is determined to need to be reduced to 160mg, 36 participants will be accrued at 160mg. We expect a participant dropout rate of less than 5%.

